5.5 ENDPOINTS

Variable	Role	Data source(s)	Operational definition
Patient demographics	Baseline characteristic, potential confounder, subgroup identifier	Patient EHR	
• Date of birth• Sex• Date of death
Clinical characteristics	Baseline characteristic, potential confounder, subgroup identifier	Patient EHR	
• Date of ABC/MBC diagnosis• Age at ABC/MBC diagnosis (years)• ECOG performance score at index date (0, 1, 2, 3, 4)• ESAS• Date of last follow-up• Organ level metastatic sites (bone, brain, lungs, liver; number of sites)• Tumour stage at initial breast cancer diagnosis (I, II, III, IV, Unknown)• Tumour grade

PFIZER CONFIDENTIAL

			
 • Tumour histology • ER and PR receptor status (Positive, Negative, Unknown) • HER2 status (Positive, Negative, Unknown) • Concomitant LHRH agonists
Comorbidities	Baseline characteristic, potential confounder, subgroup identifier	Patient EHR	
 • Atrial fibrillation • Hypertension • Coronary Artery Disease/Myocardial infarction/Angina • Diabetes Mellitus • Stroke
Treatments	Exposure	Patient EHR	
 • Systemic Therapies (therapy start and stop date including combination therapies, and line of therapy) • Surgeries • Radiation Treatment
Clinical outcomes	Outcome	Patient EHR	
 • TTNT1 • TTNT2 • TTC • Overall Survival (landmark 3y)

ECOG, Eastern Cooperative Oncology Group; EHR, Electronic Health Record; ER, Estrogen Receptor; ESAS, Edmonton Symptom Assessment System; HER2, Human Epidermal Receptor Growth Factor 2; LHRH, Luteinizing Hormone-Releasing Hormone; PR, Progesterone Receptor; TTC, time from date of ABC/MBC diagnosis to starting chemotherapy; TTNT1, length of treatment for the first line; TTNT2, length of treatment for the second line

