7 STATISTICAL METHODOLOGY AND STATISTICAL ANALYSES

7.1 STATISTICAL METHODS

The following analyses are expected to be conducted in R.

Analyses for continuous Data

Continuous variables will be described by the number of patients with valid/non-missing observations using mean, standard deviation (SD), quantiles (Q1, median, Q3), minimum and maximum.

Analyses for Categorical Data

Categorical variables will be described by frequencies and related percentages.

Analyses for time to event end points.

Time to event variables will be analyzed using Kaplan-Meier curves (TTNT1, TTNT2, TTC, OS). Numbers at risk and cumulative incidence will be reported for each curve.

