[REDACTED] if deemed necessary, to explore differences between variables such as clinical characteristics, baseline co-morbidities, types of treatments, lines of therapy, or 'responders' (i.e., patients who remained on treatment for 3 months or longer) and 'non-responders' (i.e., patients who remained on treatment for less than 3 months). Subgroup analyses may be conducted on pre-menopausal patients, if appropriate. Short term responders will be defined as those who are on first line therapy for up to 3 to 6 months and long term responders as those who are on first line therapy for over 6 months; the exact most appropriate definition will be defined after consulting with clinicians. The above-mentioned analyses will use the following or similar R packages: 'survminer' and 'tables'.

Type	Supports Protocol Objective Number	Endpoint	Population	Statistical Method/Test	Covariates used	Method of adjustment for missing values	Role of the analysis related to study objectives
CCI	[REDACTED]	[REDACTED]	[REDACTED]	[REDACTED]	[REDACTED]	[REDACTED]	[REDACTED]
	[REDACTED]	[REDACTED]	[REDACTED]	[REDACTED]	[REDACTED]	[REDACTED]	[REDACTED]

PFIZER CONFIDENTIAL

[figure not shown]
^a Patients who are potentially pre-menopausal are included in this subgroup. Please refer to section 4.4 of this document for further details about how this group is defined.

CCI

Type	Supports Protocol Objective Number	Endpoint	Population	Statistical Method/Test	Covariates used	Method of adjustment for missing values	Role of the analysis related to study objectives
CCI							

PFIZER CONFIDENTIAL

CCI	[REDACTED]						
-----	------------	------------	------------	------------	------------	------------	------------

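### SAP 7.2 lets time-to-event outcomes be explored by responder status, which is known only 3 or 6 months into follow-up, with no visible guard against guaranteed-time bias

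*SAP*

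**What the plan says.** The time-to-event part of SAP 7.2 allows exploration "if deemed necessary, to explore differences between variables such as clinical characteristics, baseline co-morbidities, types of treatments, lines of therapy", and the same list ends with responders, defined as "patients who remained on treatment for 3 months or longer", and non-responders, defined as "patients who remained on treatment for less than 3 months". The definition does not say which line of treatment counts. The opening of that sentence is redacted, and so are the analysis tables that follow.

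The paragraph adds a second split: "Short term responders will be defined as those who are on first line therapy for up to 3 to 6 months", against long-term responders with more than 6 months. The final cut is left to discussion with clinicians. The paragraph names an R package for survival curves.

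SAP 7.1 sets the method: "Time to event variables will be analyzed using Kaplan-Meier curves (TTNT1, TTNT2, TTC, OS"). SAP 5.5 supplies the definitions that matter here: "TTNT1, length of treatment for the first line" and "TTC, time from date of ABC/MBC diagnosis to starting chemotherapy". The only landmark in the visible text is "Overall Survival (landmark 3y"), which is an outcome and not a starting point for comparing responders.

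The summary in SAP 7.2.2 gives systemic therapies as the only strata for TTNT1, TTNT2, TTC and OS, and labels these outcomes exploratory. Figures 6 to 13 are by type of treatment. Responder type appears in the shells only in Tables 3, 9 and 10.

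**The concern.** Time on treatment is measured during the follow-up over which the outcomes are counted. A patient who dies on treatment before 3 months becomes a non-responder because of the death. A responder, by construction, was alive for at least 3 months. A Kaplan-Meier OS curve that starts at treatment or diagnosis therefore stays at 100% for responders over their first 3 months on treatment, while every death on treatment in that time falls to the other group. The curves separate even if staying on treatment has nothing to do with survival.

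The same holds for the 6-month split. Long-term responders have 6 guaranteed months. If short-term means 3 to 6 months, that group has only 3.

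The group labels invite a reader to take the gap as benefit. Having no hypothesis tests does not help, because the distortion is in the curves and medians themselves. With fewer than 54 patients expected, a few early deaths could shape the picture.

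**Working it through.** The plan has no figure of its own to reproduce: no power, event count or hazard ratio is stated. The check has two parts.

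**1. Which endpoints are affected**

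- OS from treatment start or diagnosis: affected, with at least 3 (or 6) guaranteed months.
- TTC, which runs from diagnosis: affected when the qualifying treatment is not chemotherapy, since staying on it for 3 months means that chemotherapy has not yet started. Not affected this way when the qualifying treatment is chemotherapy.
- TTNT1: circular if status is set on first line, because outcome and grouping are the same quantity. At 3 months, 100% of responders and 0% of non-responders are still on first-line treatment.
- TTNT2: no guaranteed time if status is set on first line and the clock starts at second line.

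**2. Size for OS when there is no effect**

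Inputs from Protocol section 7:

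- Median time to stopping treatment of 24.8 or 9.2 months. These are the cited PALOMA-2 and PALOMA-3 median PFS values for the palbociclib arms, *assumed* here to stand for time to stopping.
- Survival of 95.6% at 12 months (cited Canadian chart review, palbociclib + AI) or 22% at 5 years (cited for stage IV disease).
- Cohort below 0.30 × 180 = 54 (reason given in the amendment tables of both documents).

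Assumed model: exponential time to stopping with hazard c, exponential time to death with hazard d, independent of each other, and the same d for every patient. So the true hazard ratio is 1.

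- c = ln 2 / median: 0.0279 or 0.0753 per month.
- d = −ln(0.956)/12 = 0.00375, or −ln(0.22)/60 = 0.0252 per month.
- Share of non-responders: 1 − exp(−3(c + d)).
- Responder OS at t ≥ 3: exp(−d(t − 3)).
- Non-responder OS at t ≥ 3: exp(−dt) × (1 − exp(−3c)) / (1 − exp(−3(c + d))).

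Example (24.8 months; 95.6%): share = 1 − exp(−0.0951) = 0.091. Non-responder OS at 12 months = 0.956 × 0.0804 / 0.0907 = 0.848. Responder OS = exp(−0.00375 × 9) = 0.967.

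Hazard ratios are Cox fits to 60,000 simulated patients per scenario, with administrative censoring uniform on 3 to 69 months.

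| Median stop; survival input | Non-responders (of 54) | 3-month OS, resp. vs non-resp. | 12-month OS, resp. vs non-resp. | Gap at 12 months | Naive HR | HR after 3-month landmark |
|---|---|---|---|---|---|---|
| 24.8; 95.6% at 12 mo | 9.1% (5) | 100 vs 87.7% | 96.7 vs 84.8% | 11.9 | 0.45 | 1.01 |
| 9.2; 95.6% at 12 mo | 21.1% (11) | 100 vs 94.7% | 96.7 vs 91.6% | 5.1 | 0.67 | 1.00 |
| 24.8; 22% at 5 y | 14.7% (8) | 100 vs 50.6% | 79.7 vs 40.3% | 39.4 | 0.37 | 0.98 |
| 9.2; 22% at 5 y | 26.0% (14) | 100 vs 72.0% | 79.7 vs 57.4% | 22.3 | 0.58 | 1.00 |

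The standard error of the log HR after the landmark is 0.015 to 0.045, so all four landmark values agree with 1.

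Expected deaths in the first 3 months among 54 patients: 54 × (1 − exp(−3d)) = 0.6 with the 95.6% input and 3.9 with the 22% input.

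**The case against.** The strongest reply is that the plan may never produce the curve in question. The comparison is conditional and exploratory. The opening of the sentence and the analysis tables, which would state the outcome, population and time origin, are redacted. The 7.2.2 strata and Figures 6 to 13 do not include responder status. All of this stands. A reader might infer that the SAP commits to OS curves by responder status, or that it has no landmark rule anywhere. The documents support neither reading; what can be said is that the visible text permits the comparison and shows no safeguard.

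A reader might also infer that all four endpoints are biased. TTNT2, and TTC where the qualifying treatment is chemotherapy, need not be.

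On size, assuming a median OS of 30 to 48 months gives gaps of 16 to 38 points, and a reader might take 16 as the minimum. The protocol's cited 12-month survival of 95.6% gives gaps as small as about 5 points, and with that input fewer than one death is expected in the first 3 months.

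The reply does not remove the point. The grouping is printed under the time-to-event heading, with Kaplan-Meier as the method and a survival-curve package named. Whatever the redacted words say, the groups are defined by time on treatment.

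**Conclusion.** The point holds in conditional form. If OS is shown from treatment start or diagnosis by responder status, or by short- versus long-term status, the favoured group has at least 3 or 6 guaranteed months alive and will look better without any effect. TTC shares the problem when the qualifying treatment is not chemotherapy. TTNT1 by first-line responder status carries no information beyond the definition.

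Under the no-effect model the spurious 12-month OS gap is about 5 to 39 points, with a naive hazard ratio of about 0.37 to 0.67. These sizes rest on exponential and independent times, and on PFS standing in for time to stopping treatment. They are illustrative; the direction follows from the group definitions alone. The analysis is exploratory and may not be run, but a sentence or two in the SAP would settle the matter.

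**What to change.** Add to SAP 7.2, for any OS or TTC curve by responder status:

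- Set the landmark at 3 months after the start of the qualifying treatment, and say which line that is. For short versus long term, set it at 6 months after the start of first-line therapy.
- Include only patients who are alive, under follow-up and free of the endpoint at the landmark. Fix their status then and restart the clock there. Treating status as time-varying is an alternative.
- Report how many patients die, and how many are censored, before the landmark.
- Do not compare TTNT1 by responder status.

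If the redacted text already contains such a rule, a cross-reference is enough. A landmark removes the guaranteed time only. Patients who stay on treatment may still differ from those who stop, so the curves remain descriptive.

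The cost is SAP wording and some patients. Those with an event or censored before the landmark drop out. Because data end on 01 October 2021, this includes anyone starting the qualifying treatment after about 01 July 2021 for the 3-month landmark, or first-line therapy after about 01 April 2021 for the 6-month landmark. The loss comes from an expected cohort below 54, which is a reason to report the counts.

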^b Includes patients who received Palbociclib treatment and who are potentially in pre-menopause. Please refer to section 4.4 of this document for further details about how this group is defined.

Table 3: Demographics and Baseline characteristics stratified by type of responder

Variables	Short term responders (n=) ^a	Long term responders (n=) ^b
Age		
N Mean (SD) Median Q1,Q3 Minimum-Maximum		
Sex		

PFIZER CONFIDENTIAL

Female		
Male		
Unknown		
ECOG		
0		
1		
2		
3		
4		
Unknown		
Organ level metastatic site		
Bone		
Brain		
Lungs		
Liver		
Number of metastatic sites		
0		
1		
2		
3		
4		
Comorbidities		
Atrial fibrillation		
Hypertension		
Coronary Artery		
Disease/ Myocardial infarction /Angina		
Diabetes Mellitus		
Stroke		
Tumour stage at diagnosis		
I		
II		
III		
IV		
Unknown		
Tumour grade		
1		
2		
3		
Unknown		
Tumour histology		
Lobular Carcinoma		
Ductal carcinoma		
Mixed		

PFIZER CONFIDENTIAL

DCIS		
LCIS		
Other		
Unknown		
ER Receptor status		
Positive		
Negative		
Unknown		
PR Receptor status		
Positive		
Negative		
Unknown		

^a Defined as those who are on first line therapy for up to 3-6 months

^b Defined as those who are on first line therapy for more than 6 months

Table 4: Demographics and Baseline characteristics stratified by pre and post CDK subgroups

Variables	Pre-CDK ^a (N=)	Post CDK ^b (N=)
Age		
N		
Mean (SD)		
Median		
Q1, Q3		
Minimum-Maximum		
Sex		
Female		
Male		
Unknown		
ECOG		
0		
1		
2		
3		
4		
Unknown		
Organ level metastatic site		
Bone		
Brain		
Lungs		
Liver		
Number of metastatic sites		
0		
1		

PFIZER CONFIDENTIAL

	2		
	3		
	4		
Comorbidities			
	Atrial fibrillation		
	Hypertension		
	Coronary Artery		
	Disease/Myocardial infarction/Angina		
	Diabetes Mellitus		
	Stroke		
Tumour stage at diagnosis			
	I		
	II		
	III		
	IV		
	Unknown		
Tumour grade			
	1		
	2		
	3		
	Unknown		
Tumour histology			
	Lobular Carcinoma		
	Ductal carcinoma		
	Mixed		
	DCIS		
	LCIS		
	Other		
	Unknown		
ER Receptor status			
	Positive		
	Negative		
	Unknown		
PR Receptor status			
	Positive		
	Negative		
	Unknown		

^a Defined as treatment started between January 2016-May 2016

^b Defined as treatment started between January 2019- May 2019

Table 5: Demographics and Baseline characteristics stratified by time of diagnosis.

Variables	Before COVID-19 ^a (N=)	During COVID-19 ^b (N=)
-----------	-----------------------------------	-----------------------------------

PFIZER CONFIDENTIAL

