	Line 1	Line 2	Line 3	Line 1	Line 2	Line 3
Chemotherapy N, Mean Tx duration (SD)						
Chemo type 1, n (%)						
Chemo type 2, n (%)						
...						
Targeted therapy N, Mean Tx duration (SD)						
Targeted type 1, n (%)						
Targeted type 2, n (%)						
...						
...						

^a Defined as treatment started between January 2016-May 2016^b Defined as treatment started between January 2019- May 2019

Table 8: Sequencing of therapies after CDK 4/6 inhibitor

[figure not shown]
	Overall (N=)
Post-CDK received in L1	
Medicinal product name 1, n (%)	
Medicinal product name 2, n (%)	
...	
Post-CDK received in L2	
Medicinal product name 1, n (%)	
Medicinal product name 2, n (%)	
...	
Post-CDK received in L3	
Medicinal product name 1, n (%)	
Medicinal product name 2, n (%)	
...	

Bar charts

Figure 5: Classes of treatments over time in all patients. Please refer to Figure.1 for reference as to how bar charts will look. Similar plots will be created for all lines of therapy.

PFIZER CONFIDENTIAL

Time to event analyses in all patients:

Figure 6: TTNT1 in all patients by type of treatment

Figure 7: TTNT2 in all patients by type of treatment

Figure 8: TTC in all patients by type of treatment

Figure 9: Overall Survival in all patients by type of treatment

Table 9: Length of Line 1 treatment in short term vs long term responders

Variables	Short term responders (n=) ^a	Long term responders (n=) ^b
Chemotherapy N, Mean Tx duration (SD)		
Chemo type 1		
N		
Mean (SD)		
Median		
Q1,Q3		
Minimum-Maximum		
Chemo type 2		
N		
Mean (SD)		
Median		
Q1,Q3		
Minimum-Maximum		
...		
Targeted therapy N, Mean Tx duration (SD)		
Targeted type 1		
N		
Mean (SD)		
Median		
Q1,Q3		
Minimum-Maximum		
Targeted type 2		
N		
Mean (SD)		
Median		
Q1,Q3		
Minimum-Maximum		
...		

^a Defined as those who are on first line therapy for up to 3 to 6 months

^b Defined as those who are on first line therapy for more than 6 months

Time to event analyses in pre-menopausal patients:

Figure 10: TTNT1 in patients who are potentially in pre-menopause by type of treatment

Figure 11: TTNT2 in patients who are potentially in pre-menopause by type of treatment

Figure 12: TTC in patients who are potentially in pre-menopause by type of treatment

Figure 13: Overall Survival in patients who are potentially in pre-menopause by type of treatment

Table 10: Length of Line 1 treatment in short term vs long term responders in pre-menopausal patients^a

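### Tables 9 and 10 summarise first-line duration in groups cut on that same duration, with plain means and no readable rule for treatment still ongoing at the 1 October 2021 cut-off

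*SAP*

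**What the plan says.** SAP 7.2 (time to event analysis) defines the groups by time on first-line therapy alone: "Short term responders will be defined as those who are on first line therapy for up to 3 to 6 months", with long-term responders being those on it for over 6 months. It adds that "the exact most appropriate definition will be defined after consulting with clinicians". The same paragraph separates responders (3 months or longer on treatment) from non-responders ("i.e., patients who remained on treatment for less than 3 months").

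Three table shells in SAP 8 use the two groups, each with only a short-term and a long-term column:

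- Table 3 gives baseline characteristics. Its footnote reads "Defined as those who are on first line therapy for up to 3-6 months".
- Table 9 is "Length of Line 1 treatment in short term vs long term responders".
- Table 10 is "Length of Line 1 treatment in short term vs long term responders in pre-menopausal patients".

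Tables 9 and 10 list, per drug class and type, N, mean (SD), median, quartiles and minimum to maximum. Nothing in the shells or footnotes mentions ongoing treatment.

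Elsewhere Line 1 length is a censored quantity. SAP 5.5 defines TTNT1 as the length of first-line treatment, and SAP 7.1 and 7.2.2 assign it Kaplan-Meier curves. Figure 6 ("TTNT1 in all patients by type of treatment") and Figure 10 ("TTNT1 in patients who are potentially in pre-menopause by type of treatment") are already planned. Protocol 9.7 leaves censoring rules to the SAP. There, section 5.1 and much of the time-to-event text are redacted, and the heading for further endpoint definitions in Appendix 1 has no text under it.

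**The concern.** The variable that forms the groups is also the variable summarised. Every long-term value exceeds 6 months and no short-term value does, so the contrast in length is not a finding. According to the amendment log, the objective that was moved is itself worded as length of treatment in short- versus long-term responders. Tables 9 and 10 are its visible output, so a reader may well take the gap as a result.

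Follow-up ends on 1 October 2021, three months after the last eligible diagnosis. A patient still on first line with less than 6 months of follow-up has not shown a short duration. If observed time is used, that patient nevertheless enters the short-term column. A patient ongoing beyond 6 months is correctly long-term, but the recorded length is cut short and pulls the column mean down.

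Who is counted is also unclear. Up to 3 to 6 months can mean 3 to 6 months, or any length up to 6. On the first reading patients under 3 months are in neither column; on the second they are in the short-term one.

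**Working it through.** The plan gives no figure to reproduce: Protocol 9.5 states that sample size calculations do not apply. The overlap of grouping and outcome needs no arithmetic. The calculation below only shows how large the ongoing-treatment problem could be.

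**Inputs**

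- Diagnosis from 1 January 2016 to 1 July 2021 (2008 days) and cut-off 1 October 2021 (Protocol 9.2.1 and 9.4). Minimum follow-up is 92 days. I take follow-up C as uniform from 3 to 69 months, first line starting at diagnosis, and no loss to follow-up.
- N is below 0.30 × 180 = 54 (amendment logs). I use 54 as an upper bound.
- Assumed first-line median: 14.5 or 24.8 months. These are the two PFS medians of the phase III letrozole trial in Protocol 7 (placebo and palbociclib arms), used as stand-ins.
- Assumed survival median: 60 × ln 2 / −ln 0.22 = 27.5 months (22% at 5 years, stage IV) or 12 × ln 2 / −ln 0.956 = 184.9 months (95.6% at 12 months, Canadian chart review). Both rates are in Protocol 7. Death is taken to end first line.

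**Formulas**, with exponential times and rate h = ln 2/first-line median + ln 2/survival median:

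- Ongoing share of the over-6 group: p = (1 − e^(−63h)) / (63h)
- Completed mean of that group: 6 + 1/h
- Mean if ongoing durations stop at cut-off: 6 + (1 − p)/h, so the shortfall is p/h
- Patients in the 3 to 6 month band only because follow-up stopped: 54 × (e^(−3h) − e^(−6h)) / (66h)
- All patients in that band: 54 × (e^(−3h) − (63/66)e^(−6h))
- Patients under 3 months: 54 × (1 − e^(−3h))

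**Results**

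| First-line / survival median (months) | h | p | Completed mean | Tabulated mean | Shortfall | Band by censoring / band total | Under 3 months |
|---|---|---|---|---|---|---|---|
| 14.5 / 27.5 | 0.0730 | 21.5% | 19.7 | 16.7 | 2.9 | 1.8 / 10.1 | 10.6 |
| 24.8 / 27.5 | 0.0532 | 28.8% | 24.8 | 19.4 | 5.4 | 1.9 / 8.6 | 8.0 |
| 14.5 / 184.9 | 0.0516 | 29.6% | 25.4 | 19.7 | 5.7 | 2.0 / 8.4 | 7.7 |
| 24.8 / 184.9 | 0.0317 | 43.3% | 37.5 | 23.9 | 13.7 | 2.1 / 6.5 | 4.9 |

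Worked line, last row: 63h = 1.997, p = (1 − 0.136)/1.997 = 0.433, 1/h = 31.5, shortfall = 0.433 × 31.5 = 13.7 months.

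**Sensitivity.** If death is ignored (h = ln 2/first-line median), p is 32% to 47% and the tabulated means are 20.3 and 24.9 months against completed means of 26.9 and 41.8. A simulation of 2,000,000 patients without death gave the same values to within 0.1 month. Using only ended treatments does not help: the simulated means were then 18.8 and 21.6 months.

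**Date check.** Patients diagnosed after 1 April 2021 cannot be followed beyond 6 months. That is 91/2008 = 4.5% of the window, or 2.4 of 54, in line with the roughly 2 patients above.

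**The case against.** - **The footnotes already say that time on first line defines the groups, and no text calls the gap a result.** This is true. The per-drug rows also show which drugs fall in which group, which is real information. What remains is that the tables' titles and statistics present duration as the quantity of interest.
- **A censoring rule may be redacted.** This stands as a limit. The SAP amendment log records a change of an end date to last follow-up or death, so some end-of-observation convention probably exists. A reader might infer that the plan counts ongoing treatment as ended; the readable text does not show that. Even so, a censoring rule for the curves would not make a plain mean or SD account for ongoing treatment.
- **The bands can be read coherently:** under 3 months is a non-responder, 3 to 6 short-term, over 6 long-term, so Tables 3, 9 and 10 omit non-responders by design. This is plausible, and the SAP calls the definition provisional. But the words up to still allow the other reading, and no time is set for the decision. Alone, this would be only a missing detail.
- **The assumed durations may be too short.** The Canadian chart review in Protocol 7 reports 90.3% progression-free at 12 months and 91% at 6 months. Under an exponential these imply medians of about 82 and 44 months. Then only 1 − 0.903^(1/4) = 2.5% to 1 − 0.91^(1/2) = 4.6% of patients (1.4 to 2.5 of 54) would be under 3 months, so that question shrinks. The ongoing share would rise, to 63% to 77% with death ignored, so the main point grows.

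**Conclusion.** The point holds as a minor one. On readable text, Tables 9 and 10 summarise the variable that defines their columns, with statistics that do not handle ongoing treatment. If observed durations are used, about 2 of 54 patients would sit in the 3 to 6 month band only because follow-up stopped. Some 22% to 43% of the over-6-month group would be ongoing, and its mean would be about 3 to 14 months below the completed mean. These sizes are illustrations that rest on exponential durations, PFS medians as stand-ins for first-line length, uniform diagnosis dates, no loss to follow-up, and 54 as an upper bound on N.

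A reader might also infer that survival or time to chemotherapy will be compared between responder groups, which would give the longer group guaranteed event-free time. The documents do not support this. No listed Kaplan-Meier figure or stratum uses these groups, and the method of the optional exploration that names responders and non-responders is redacted.

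The outputs are exploratory and descriptive, with no hypothesis test, and the primary objective is unaffected. The harm is to group membership in three tables and to what may be concluded from two of them.

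**What to change.** 1. In SAP 7.2 and the footnotes of Tables 3, 9 and 10, classify as short-term only patients whose first line ended within the band. Show patients last observed on first line before the 6-month cut-point in a separate count labelled not classifiable.
2. In Tables 9 and 10, give the number still on treatment in each column and draw no short- versus long-term conclusion on duration. Take Line 1 length from Kaplan-Meier Figures 6 and 10, which are already planned.
3. Have the clinicians settle the definition before the data are analysed. Reconcile the short-term band with the non-responder wording, and say in which column, if any, patients under 3 months belong. The choice of cut-point is theirs.

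The cost is SAP wording, footnotes and count rows, with no new data and no new figure. The downside is that a few patients (about 2 of 54 in the illustration) leave the two columns, and the tables no longer support a statement on duration by group.
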